#### 5.7 Study Procedures

#### 5.7.1 Randomization and blinding

This study will be a non-randomized pilot observational study.

#### 5.7.2 Study monitoring

#### 1) Required end points during study drug infusion

• Mean Arterial Pressure:

The recipient's mean arterial pressure (MAP) will be monitored at 1 minute intervals during study drug infusion followed by 15 minute intervals for 1 hour.

• Nitrite and metabolite levels:

Blood samples will be obtained prior to the infusion; at 5, 30, and 60 minutes during the infusion; and at 5, 10, 30, 60, 90, 150 after the infusion to measure plasma and whole blood nitrite, plasma nitrate, red cell iron-nitrosyl-hemoglobin, S-nitroso-hemoglobin and methemoglobin concentrations. However, no sample will be sent for methemoglobin concentration prior to drug infusion. Blood samples will also be obtained every 24 hours for two days for future exploratory biomarker/proteomic studies which would include evaluation of IL6, IL $\beta$ , TNF-a, iNOS and COX-2. Nitrite levels will be measured by established methodologies (ozone-based reductive chemiluminescence) routinely performed in [name] NO Metabolomics Core facility.

2) Required end points post study drug infusion to hospital discharge

Following administration of the Sodium Nitrite, the study subjects will continue to receive usual care for their condition consistent with local transplant treatment protocols. The study will not introduce any modification to the normal care algorithms. Day 0 ( $D_0$ ) will be defined as the day of transplantation and reperfusion. Subsequent study days will be numbered sequentially. The following parameters will be required for collection prospectively. They will be obtained specifically for the study protocol if not requested by the treating physician. If requested by the treating physician the parameters will be recorded from the medical record. Specific parameters required to be monitored following lung transplantation/reperfusion will include:

• Arterial blood gas measurements from D0 to D3

The  $Pa0_2/FiO_2$  ratio and oxygenation index will be calculated based upon an arterial blood gas at D0 (within 6 hours of reperfusion), and D1, D2, and D3. The initial measurement (D0) will be obtained on a FiO2 of 1.0 and PEEP of 5 while on mechanical ventilation. Subsequent measurements will be obtained on the prescribed ventilator settings. Ventilator parameters will be obtained with each blood gas determination. **There will be no arterial blood gas measurement on days patient is extubated.** 

• Chest radiography from D0 to D3

Plain film portable chest radiography will be obtained on D0 (within 6 hours of reperfusion), and D1, D2, and D3. All chest radiography will be referred to a radiology core for independent review and classification independent of the review required for clinical documentation.

Grade	PaO2/FiO2	Radiograph	
0	>300	Absent	
1	>300	Present	
2	200-300	Present	
3	<200	Present	

The primary end point of PGD will be scored using the following criteria:

The absence of pulmonary infiltrates on plain film radiograph will be assigned Grade 0 independent of the PaO2/FiO2 ratio. All extubated patients will be graded as 0 or 1 based upon the interpretation of the chest radiograph. The need for extracorporeal support and/or inhaled nitric oxide will be documented and automatically assigned a Grade III classification.

The diagnosis of Primary Graft Dysfunction (PGD) requires the exclusion of alternative conditions, which might produce a similar radiographic and physiologic pattern including hyperacute rejection, cardiogenic pulmonary edema, venous anastomotic obstruction, and allograft infection. Exclusion of these conditions will be made by a PGD grading committee composed of transplant physicians not involved in the patient's care at the time of transplant until hospital discharge. Medical records will be reviewed within six to eight weeks of transplantation by the committee to classify PGD.

• Sequential Organ Failure Assessment Score (SOFA):

The SOFA score is a recognized ICU scoring system to define the extent of the patient's organ failure. The scoring system has an individual component score for each of 6 organ systems including **respiratory**, **cardiovascular**, **hepatic**, **coagulation**, **renal** and **neurological** systems . The SOFA Score will be obtained daily at D1, D2, D3, and D4.

- Ventilator Free Days (VFD): Defined as the number of days off mechanical ventilationat 8am through D30 post transplantation.
- ICU Free Days (IFD): Defined as the number of days outside the ICU through D30 post transplantation.
- Hospital Days: Defined as the total number of acute and long term acute (LTAC) hospital days during the index transplant admission.
- Outcome at 90 days: Patient clinical status at D90 post transplantation including living or deceased, and location. To confirm clinical status of patient on Day 90 post transplant as living or deceased and if living current location, a follow up call with made to the patient or the family n day 90 +/- 7 days.

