#### 2.4 Endpoints

#### Primary Endpoints Analysis

- The primary endpoint for the safety of Sodium Nitrite administration will be assessed by measurement of methemoglobin levels and mean arterial pressure during the nitrite infusion in the transplant recipient.
- The primary endpoint for the efficacy of Sodium Nitrite infusion will be the incidence of grades 2 and 3 PGD using the International Society for Heart and lung transplant (ISHLT) criteria for PGD based upon the worst value obtained over the initial 72 hours post lung reperfusion (T0-72).

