#### Organ Reperfusion to Recipient

A specifically labeled frozen syringe of prepared stock Sodium Nitrite solution (1.33 mL, 30 mg/,L) will used by the UPMC pharmacy to prepare a 40 mg Sodium Nitrite in a 250 ML infusion

bag of normal saline (i.e., 0.16 mg/mL) The entire volume of this bag will be used to administer to the patient at the time of Organ Perfusion.

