#### Organ Implantation prior to Reperfusion

At the time of transplant, the first donor lung will be flushed with a cold pneumoplegia solution after the bronchial (1st) anastomosis. The pneumoplegia solution used clinically at UPMC is a 50% Dextrose/autologous blood preparation, which includes Nitroglycerine, Verapamil and Heparin (refer to Appendix C for description of UPMC pneumoplegia solution); and the Sodium Nitrite will be added just prior to use. A second flush of pneumoplegia solution will occur after the PV (3rd, last) anastomosis. The identical pneumoplegia solution as outlined above will be used for the second flush, but at a temperature range of 34- 38 °C. The same process of flushing with pneumoplegia solution will be followed for the second donor lung.

To the recipient at the time of reperfusion:

Sodium Nitrite will be delivered intravenously to the recipient *immediately* prior to the first lung reperfusion as a single infusion of Infuse at 4 mL/min for the first 30 min, followed by 2.2 mL/min for the next 60 min.

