#### 5.8 Safety Assessment

The primary safety assessment will be based upon measured methemoglobin levels and hemodynamic indices during the Sodium Nitrite infusion. Because of the exploratory nature of this trial, all potential Adverse Events will be recorded for review.

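### The primary methemoglobin endpoint is worded as levels during the infusion, yet the last in-infusion sample is at 60 of 90 minutes and the plan conflicts on whether the later samples count

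*Combined protocol and SAP*

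**What the plan says.** Section 2.4 (Primary Endpoints Analysis) assesses the primary safety endpoint by "methemoglobin levels and mean arterial pressure during the nitrite infusion in the transplant recipient". Section 5.8 repeats the window: the primary safety assessment rests on "measured methemoglobin levels and hemodynamic indices during the Sodium Nitrite infusion". The primary objective in section 2.3 names the same two measures without a time window.

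Section 5.5 gives the recipient schedule: "Infuse at 4 mL/min for the first 30 min, followed by 2.2 mL/min for the next 60 min", which is 90 minutes if uninterrupted. Section 5.6 allows pauses, which lengthen it.

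Section 5.7.2, item 1, sets the blood sampling: one pre-infusion draw, then "at 5, 30, and 60 minutes during the infusion; and at 5, 10, 30, 60, 90, 150 after the infusion". The last group carries no unit; I take it as minutes. Methemoglobin is measured at all of these times except the first, since "no sample will be sent for methemoglobin concentration prior to drug infusion". The heading of item 1 refers to end points required during the infusion, yet the list under it runs to 150 minutes afterwards. Item 2, which covers the period from the end of the infusion to discharge, lists no methemoglobin.

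The plan does not say which summary of the repeated methemoglobin values (maximum, mean, proportion above a level) is the endpoint.

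**The concern.** Methemoglobin forms while nitrite is present and is cleared afterwards, so its peak can be expected to lag behind that of nitrite. A window that closes with the infusion, with its last sample 30 minutes before the close, is then likely to miss the peak. On a literal reading of sections 2.4 and 5.8, the primary safety result would rest on three values per subject in eight subjects, all from the first two thirds of dosing, while six later values are measured but left out.

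The error would run in the favourable direction, in a study whose primary objective is safety and in a population where section 8.1 says nitrite safety is not yet established. Because the wording conflicts and no summary measure is fixed, the window could also be chosen after the data are seen.

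**Working it through.** **Step 1. Reproduce the plan's own figures.** Section 5.4 puts 40 mg in a 250 mL "bag of normal saline (i.e., 0.16 mg/mL"), all of which is to be given. From section 5.5:

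- Volume = 4 × 30 + 2.2 × 60 = 120 + 132 = 252 mL.
- Dose = 252 × 0.16 = 40.3 mg, which agrees with 40 mg in 250 mL apart from rounding.
- Given by 60 minutes: 120 + 2.2 × 30 = 186 mL. 186/252 = 74%, so 26% follows the last in-infusion sample.

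**Step 2. Nitrite.** I use a one-compartment model with an uninterrupted infusion and the 42-minute half-life from section 8.1: k = ln 2/42 = 0.0165 per minute. Input is 4 × 0.16 = 0.64 mg/min for 30 minutes, then 2.2 × 0.16 = 0.352 mg/min for 60 minutes. Over 30 minutes, e^(−30k) = 0.6095.

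- A(30) = (0.64/k)(1 − 0.6095) = 15.14 mg
- A(60) = 15.14 × 0.6095 + (0.352/k)(1 − 0.6095) = 17.56 mg
- A(90) = 17.56 × 0.6095 + 8.33 = 19.03 mg, the peak
- A(95) = 19.03 × e^(−5k) = 17.52 mg

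Relative to the peak: 80% at 30 minutes, 92% at 60 minutes, 92% at 5 minutes after the end. Nitrite is still rising when the infusion stops.

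**Step 3. Methemoglobin.** The model is dM/dt = A(t) − (ln 2/h)M with M(0) = 0; the formation constant cancels in the ratios. The half-life h is my assumption, varied over 15 to 180 minutes. The ratios describe the rise caused by the infusion.

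| Assumed h (min) | Peak, minutes after end of infusion | 60-minute sample, % of peak | Best scheduled sample, % of peak |
|---|---|---|---|
| 15 | 5 | 82 | >99.9 (5 min after) |
| 30 | 14 | 70 | 99.7 (10 min after) |
| 60 | 31 | 58 | >99.9 (30 min after) |
| 120 | 55 | 48 | 99.9 (60 min after) |
| 180 | 71 | 44 | 99.6 (60 min after) |

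The 60-minute value is always the largest of the three in-infusion values.

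**Step 4. Sensitivity.** I also varied the nitrite half-life (20, 30, 42 and 60 minutes), giving 20 combinations with the five values of h. In every one the modelled methemoglobin peak came at or after the end of the infusion. The 60-minute sample read 38 to 96% of it, and the best scheduled sample at least 98%.

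**Step 5. Would an end-of-infusion draw be enough?** With a 42-minute nitrite half-life, a draw at 90 minutes with the window unchanged lifts the best in-window value to 73 to 99% of the peak. The gap comes from the window more than from the draw times.

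**The case against.** The strongest counter-argument is the heading in section 5.7.2. It groups the post-infusion methemoglobin draws with the infusion-period end points, and the block for later end points lists none. The protocol's own grouping may therefore mean that all these values count. This stands: a reader might infer that the post-infusion values are definitely excluded, but exclusion is only one reading of conflicting text. It does not remove the need to reconcile the sections, because 2.4 and 5.8 say otherwise.

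A reader might also infer that the nitrite peak is missed. It is not. The samples on either side each read about 92% of the modelled peak, and with a 20-minute half-life the modelled peak falls at the 30-minute draw. Nitrite pharmacokinetics is also a secondary objective.

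A reader might further infer that values above 3% could be hidden. The documents do not support that. Section 8.1 cites 3% as past experience, and no endpoint or rule uses it. It reports that regimens of about 40 mg stayed at or below 3%, and that about 300 mg over 10 minutes gave 5.7% in healthy volunteers. Linear scaling, a rough assumption, gives 5.7 × 40/300 ≈ 0.8%.

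Late values would not be lost to safety review either: they are measured, all potential adverse events are recorded (5.8), records are reviewed to 72 hours (10.2), and methemoglobinemia is reportable to the sponsor (10.3). Section 6 calls the analysis exploratory. This limits the consequence to what the primary result says.

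**Conclusion.** The point holds as a fault in the definition of the endpoint; the collection of methemoglobin data is adequate. Sections 2.4 and 5.8 conflict with section 5.7.2 on whether post-infusion methemoglobin counts. If the first two are applied literally, the largest value in the window would be about 44 to 82% of the modelled peak rise, an understatement of 18 to 56%.

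The draw times and the 26% of dose remaining come directly from the protocol. The size of the understatement depends on the turnover model, an uninterrupted infusion and an assumed methemoglobin half-life; the documents state neither that half-life nor a time to peak. The direction was the same in all 20 combinations tried. Nothing here suggests that high methemoglobin is expected at the planned dose.

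**What to change.** Define the primary methemoglobin endpoint in section 2.4 as each subject's maximum from the start of the infusion through the last scheduled sample, 150 minutes after it ends. Give the unit for the post-infusion times, and make sections 2.4, 5.7.2 and 5.8 agree. Say how samples are timed when the infusion is paused. The cost is a change of wording: no new draws and no change to treatment. The downside is that the reported peak may be less favourable.

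Optional and minor: timing one draw at the actual end of the infusion would remove the roughly 8% understatement of peak nitrite. It does not improve methemoglobin capture over the existing draws. The mean arterial pressure already recorded for 1 hour after the infusion can be reported separately. Merging it into the primary endpoint could mix in reperfusion effects, to which section 5.6 attributes prolonged hypotension. The missing pre-infusion methemoglobin sample is a separate gap; without it the maximum can be reported as a level but not as a change.

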#### Phase of Development: Phase II A

#### **Objectives:**

Primary Objective(s):

 To evaluate the safety of Sodium Nitrite infusion into the procured lungs and lung transplant recipient as reflected in blood mean arterial pressure and methemoglobin levels.

Secondary Objectives:

- To evaluate the efficacy of Sodium Nitrite infusion into the procured lungs and the lung transplant recipient in the prevention of grade 2-3 Primary Graft Dysfunction.
- To evaluate the efficacy of Sodium Nitrite infusion into the procured lungs and the lung transplant recipient in the prevention of delayed allograft complications including the incidence of acute rejection and BOS
- To identify the pharmacokinetic relationship of Sodium Nitrite and

metabolism of sodium nitrite in lung transplant recipients using blood sampling measures before and after drug exposure (will measure levels of plasma and whole blood nitrite, plasma nitrate, red cell iron-nitrosylhemoglobin, S-nitroso-hemoglobin and methemoglobin).

Statement of Primary Efficacy Hypothesis and Primary Analysis:

The administration of Sodium Nitrite at the time of organ procurement and transplantation will be safe and significantly reduce the rate of Primary Graft Dysfunction in patients undergoing lung transplantation.

**Planned Sample Size**: A total of 8 subjects will be enrolled into the protocol. Recruitment is expected to continue for six months.

Study Design: Phase IIA observational non-randomized cohort.

**Diagnosis and Key Patient Selection Criteria:** Males or females greater than 18 years of age or older undergoing lung transplantation.

**Treatments:** Sodium Nitrite infusion to the donor lungs and the lung transplant recipient.

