#### Secondary Objectives:

- To evaluate the efficacy of Sodium Nitrite infusion into the procured lungs and the lung transplant recipient in the prevention of grade 2-3 primary graft dysfunction.
- To evaluate the efficacy of Sodium Nitrite infusion into the procured lungs and the lung transplant recipient in the prevention of delayed allograft complications including the incidence of acute rejection and BOS.
- To identify the pharmacokinetic relationship of Sodium Nitrite and metabolism of sodium nitrite in lung transplant recipients using blood sampling measures **before and after** drug exposure (levels of plasma and whole blood nitrite, plasma nitrate, red cell ironnitrosyl-hemoglobin, S-nitroso-hemoglobin and methemoglobin will be measured).

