#### 5.3 Screening Procedures

Patients with end stage lung disease who are deemed eligible for placement on the lung transplant waiting list will be eligible for participation and written informed consent will be obtained at the time of their listing for lung transplantation. The medical records of the lung transplant patients will be reviewed for eligibility criteria by the PI and other Co- Investigators who by virtue of their role as a clinician already have the knowledge of and access to the patients' identifiable medical information. Subjects will be approached for consent after the decision has been reached to place the subject on the waiting list. After enrollment and prior to transplantation, blood will be drawn for baseline studies that include complete blood count (CBC), chemistry profile; and for storage to allow for subsequent exploratory PBMC gene expression profiling and proteomics which would include evaluation of IL6, IL $\beta$ , TNF-a, iNOS and COX-2.

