#### Organ Implantation Prior To Reperfusion

A specifically labeled frozen syringe of prepared stock Sodium Nitrite solution (12 mL, 0.16 mg/mL) will be available to the OR at the time of lung transplantation. Once thawed, the Sodium Nitrite will be added to the pneumoplegia solution to achieve a final concentration of 0.69 mg/L (10 uMolar), Thawed syringes that are not used will be discarded. The pneumoplegia solution (see Appendix C) is prepared by the UPMC Pharmacy and the Sodium Nitrite will be added immediately prior to the infusion of the pneumoplegia solution into the donor lung.

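### Methemoglobin is left out of the pre-infusion draw, so the before-and-after comparison in the secondary pharmacokinetic objective cannot be made for it in any of the 8 patients

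*Combined protocol and SAP*

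**What the plan says.** The Synopsis (Objectives) sets a secondary objective on the pharmacokinetics and "metabolism of sodium nitrite in lung transplant recipients using blood sampling measures before and after drug exposure". Section 2.3 (Secondary Objectives) repeats it, with the words for before and after in bold, and ends its list of analytes with "S-nitroso-hemoglobin and methemoglobin will be measured". The list has six measures: plasma nitrite, whole-blood nitrite, plasma nitrate, iron-nitrosyl-hemoglobin, S-nitroso-hemoglobin and methemoglobin.

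Section 5.7.2 (Nitrite and metabolite levels) sets the schedule: one draw before the infusion, three during it (5, 30 and 60 minutes) and six after it (5, 10, 30, 60, 90 and 150). It lists the same six measures and then makes one exception: "However, no sample will be sent for methemoglobin concentration prior to drug infusion". It gives no reason.

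The only other planned pre-transplant blood is in section 5.3, where "blood will be drawn for baseline studies that include complete blood count (CBC), chemistry profile", together with stored blood for exploratory gene-expression and protein work. Methemoglobin is not named there.

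The primary safety endpoint in section 2.4 "administration will be assessed by measurement of methemoglobin levels and mean arterial pressure during the nitrite infusion in the transplant recipient". Section 5.8 says the same in substance. Neither contains a change-from-baseline term.

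**The concern.** Two statements in the plan cannot both be carried out. The objective promises a before-and-after comparison that covers methemoglobin, and the schedule removes the before value for that analyte alone. The other five measures keep theirs.

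What is at stake is the rise within each patient. The study has 8 patients and no concurrent control, and section 8.1 says that the safety of nitrite in lung transplant recipients has not been established. Each patient's own pre-drug level is therefore the natural reference for describing a drug effect. Section 8.1 reports the volunteer data in that form, as a rise from baseline, and this trial could not report its own methemoglobin result that way. Mean arterial pressure, the other primary safety measure, does have a recorded pre-infusion baseline (section 5.6). A pre-infusion sample that is not assayed may not be recoverable later.

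**Working it through.** **Is there anything to reproduce?** The sample size of 8 is stated without power, effect size or precision inputs, so no plan figure can be recomputed. The check is a count of scheduled results, followed by an illustration of size.

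**Count (section 5.7.2; 8 patients from the Synopsis)**
- Draws per patient: 1 + 3 + 6 = 10. Methemoglobin is assayed at 10 − 1 = 9.
- Methemoglobin results as written: before 0 × 8 = 0; during 3 × 8 = 24; after 6 × 8 = 48; total 72.
- Patients with a before-and-after pair: 0 of 8.
- Pre-infusion results over all measures: 6 × 8 = 48 implied by the objective, against 5 × 8 = 40 in the schedule. The 8 missing are all methemoglobin.
- With methemoglobin assayed at the pre-infusion draw: 10 × 8 = 80 results and 8 of 8 pairs. The 24 during-infusion results do not change.

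**Can the primary endpoint still be measured?** Section 5.5 gives the rates: "Infuse at 4 mL/min for the first 30 min, followed by 2.2 mL/min for the next 60 min". The infusion lasts 30 + 60 = 90 minutes and delivers 4 × 30 + 2.2 × 60 = 252 mL; the 250 mL bag in section 5.4 empties at 30 + (250 − 120)/2.2 = 89.1 minutes. The 5, 30 and 60 minute draws therefore all fall within an uninterrupted infusion, and the endpoint as worded can be measured.

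**Can the 5-minute sample stand in as a baseline?** At 0.16 mg/mL (section 5.4), drug given by 5 minutes is 4 × 5 × 0.16 = 3.2 mg, and 3.2/40 = 8% of the planned 40 mg. It is an on-drug value.

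**Size, illustration only.** The one documented baseline is in section 8.1: healthy volunteers rose from 0.02% to 5.7%, or 5.68 points, after about 300 mg over 10 minutes. Two scalings to 40 mg are possible, and each needs an assumption that the documents do not establish.
- Rise proportional to dose: 5.68 × 40/300 = 0.76 points.
- Rise proportional to nitrite remaining, using the 42-minute plasma half-life in section 8.1 (k = ln 2/42 per minute): 19.03 mg remains at 90 minutes, against 276.6 mg at the end of the 10-minute reference infusion; 5.68 × 19.03/276.6 = 0.39 points.

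Reading the highest level as if it were the rise would then overstate the rise by 0.02/0.757 = 2.6% or 0.02/0.391 = 5.1% at a 0.02% baseline. The overstatement would reach 10% at a baseline of about 0.08% or 0.04% respectively. The documents do not say where lung recipients lie.

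**The case against.** The strongest reply is that the exclusion is explicit. Section 5.7.2 lists the whole panel and then carves out one analyte at one time, and a specific exception can be read as qualifying a general objective. It may well be deliberate. That changes which text should be amended, but the mismatch remains: the objective names methemoglobin in the same sentence as the before-and-after sampling.

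A second reply is that no planned analysis needs the value. This largely stands. The primary endpoint concerns levels during the infusion, the benchmarks in section 8.1 (3%, 30%, 50%) are absolute levels, and section 6 is exploratory and mentions baseline adjustment only for efficacy variables. A reader might infer that the primary safety endpoint is compromised, or that the 3% comparison is undermined. The documents support neither, since both use the level itself.

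A reader might also infer that a raised level could no longer be attributed to the drug. Section 10.3 judges relatedness by timing and by whether the drug could readily have produced the event, and it does not formally require a baseline. The nine remaining values would still show a rise and fall. What is lost is the exact within-patient change.

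Finally, the modelled rises are fragile. They extrapolate linearly from a fast infusion of about 300 mg in healthy volunteers, and the lower one applies a nitrite half-life to methemoglobin. That is correct, and the conclusion does not rest on them.

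**Conclusion.** The point holds as a conflict between a stated objective and a stated sampling rule. For methemoglobin, one of six measures in the secondary pharmacokinetic objective, the within-patient change from pre-infusion is computable in 0 of 8 patients. This rests on the written schedule alone; a routine-care value might exist, but the documents do not provide for collecting one.

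The consequence is limited to that secondary description. It would be about 0.02 points if lung recipients resembled the healthy volunteers in section 8.1; otherwise its size is unknown, and no document figure shows that it is large. The correction is worth making because it is cheap and restores something the plan says it will deliver.

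**What to change.** Delete the exclusion sentence in section 5.7.2 and assay methemoglobin at the pre-infusion draw already scheduled. Leave the primary safety endpoint as worded, and report each patient's maximum change from pre-infusion as a secondary pharmacokinetic and safety description alongside the during-infusion levels. Name the samples over which that maximum is taken.

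The cost is one assay per patient, 8 in all, taking methemoglobin assays from 72 to 80. A small extra tube may be needed, because the documents do not say whether methemoglobin is run on the same specimen as the other measures. No visit, primary endpoint or sample-size change follows.

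If the exclusion is deliberate, keep it, remove methemoglobin from the before-and-after list in the Synopsis and section 2.3, and describe the 5-minute result as an on-drug value, not a baseline. That route changes wording only and adds no assays.

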#### 5.9 Efficacy Assessment

The primary efficacy assessment will be the incidence of PGD Grade 3 or greater in comparison to age and disease-matched historical controls for the UPMC Lung Transplantation program.

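### PGD in the treated patients passes through an unmasked committee exclusion step that is not described for the historical controls, so the comparison may be biased toward benefit

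*Combined protocol and SAP*

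**What the plan says.** Section 5.7.2 first grades PGD by rule, from PaO2/FiO2 and the radiograph, with one override: "The need for extracorporeal support and/or inhaled nitric oxide will be documented and automatically assigned a Grade III classification". Films go to an independent reader: "All chest radiography will be referred to a radiology core for independent review and classification independent of the review required for clinical documentation".

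A further condition follows: "The diagnosis of Primary Graft Dysfunction (PGD) requires the exclusion of alternative conditions, which might produce a similar radiographic and physiologic pattern". The conditions named are hyperacute rejection, cardiogenic edema, venous obstruction and graft infection. On who decides, the plan says "Exclusion of these conditions will be made by a PGD grading committee composed of transplant physicians", and these physicians are to be "not involved in the patient's care at the time of transplant until hospital discharge". On timing: "Medical records will be reviewed within six to eight weeks of transplantation by the committee to classify PGD". All of this sits in the list of end points to be collected from study subjects after the nitrite infusion.

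Section 5.7.1, whose title covers blinding, says only: "This study will be a non-randomized pilot observational study". Section 5.9 sets PGD incidence "in comparison to age and disease-matched historical controls" from the UPMC program. Section 6 mentions historical controls only for comparing continuous variables. Neither section says how PGD is ascertained in controls.

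**The concern.** A comparison with historical controls is interpretable only if the outcome is established in the same way in both groups. Here one part of the outcome definition is a clinical judgement made from the chart, by reviewers who can know that every trial patient was treated. Judging that a mimic explains the picture can turn an apparent PGD case into a non-case. It cannot do the reverse.

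The plan places this judgement in the prospective follow-up of trial subjects and says nothing comparable about controls. If it is applied to one group only, the treated rate is pushed down for a reason unrelated to nitrite, and the result looks like efficacy. Enrolling more patients or reporting wider intervals would not remove such a bias; only equal ascertainment would. What is at stake is the efficacy signal. Section 2.4 calls PGD the primary efficacy endpoint, and Sections 1 and 4 say that positive results should lead to a larger trial.

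**Working it through.** **Is the review the same in both groups?** Placing the sections side by side:

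- Trial subjects: rule-based grade, core-read films, then committee review for mimics at six to eight weeks (5.7.2). Masking is not stated, and treatment is known by design (5.5, 5.7.1).
- Controls: matched on age and disease (5.9). Their number, era, grading method, film reading and exclusions are not given (5.9, 6).
- The review window runs from transplantation. Patients transplanted before the study fall outside it, unless a comparable review was done at the time or is added now. The documents mention neither.

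**Size.** The plan states no figure that could be reproduced. The inputs for an illustration are:

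- Background rate p, from the Pittsburgh row of Table 1 (Section 3; N = 76; worst grade over 0-72 hours): grades 0/1/2/3 = 21/34/20/25%, which sums to 100%. Grade 2-3 = 20 + 25 = 45%; grade 3 = 25%. The plan does not name this series as the control group.
- Share q of apparent cases that the committee excludes: not in the documents; assumed 10%, 20% and 30%.
- n = 8; nitrite assumed inert; exclusion applied to the treated group only.

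Adjudicated treated rate = p(1 - q). Spurious reduction = p × q.

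| q | Grade 2-3 rate | Reduction | Grade 3 rate | Reduction |
|---|---|---|---|---|
| 10% | 40.5% | 4.5 points | 22.5% | 2.5 points |
| 20% | 36.0% | 9.0 points | 20.0% | 5.0 points |
| 30% | 31.5% | 13.5 points | 17.5% | 7.5 points |

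Both columns are needed because Section 2.4 defines the efficacy endpoint as grades 2 and 3, while Section 5.9 compares grade 3 or greater.

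**How certain is a fall with 8 patients?** Exact binomial, n = 8, for q = 10, 20 and 30%:

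- Chance that at least one case is excluded, 1 - (1 - pq)^8: 31%, 53%, 69% for grade 2-3; 18%, 34%, 46% for grade 3.
- Chance that the observed grade 2-3 rate is below 45% (3 or fewer cases): 58%, 68%, 78%, against 48% with no exclusions.
- Chance that the observed grade 3 rate is below 25% (0 or 1 case): 43%, 50%, 58%, against 37% with no exclusions.

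**What would cancel it?** If a share u of non-cases became cases in the treated group only, for example through fuller testing, the bias disappears when u = pq/(1 - p). At q = 20%, u = 0.09/0.55 = 16.4% for grade 2-3 and 0.05/0.75 = 6.7% for grade 3.

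**Under equal review.** If both groups have the same q and p, the expected difference with an inert drug is 0 points.

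**The case against.** Several points on the other side have force.

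- *Controls may get the same exclusions.* Section 5.7.2 makes exclusion of mimics part of the PGD diagnosis, so a consistent reading of Section 5.9 would apply it to controls too. This stands to the extent that non-review of controls is partly inferred from silence. It does not settle the matter, because the only review described is tied to the study follow-up of trial subjects.
- *The committee does more than remove cases.* A reader might infer that it can only delete diagnoses. The text does not support that: its remit is to classify PGD. Only the exclusion step runs in one direction. The automatic grade III rule can raise a grade, but it belongs to the rule-based part and can be applied identically to controls.
- *The net direction is open.* Section 5.7.2 requires D0-D3 gases (except on days when the patient is extubated) and films in trial subjects, obtained for the study if not ordered clinically. With worst-value scoring, that could find more PGD than a chart review of controls would. This stands.
- *There are safeguards.* Committee members are outside the patient's care, and films go to an independent core. Both help, but neither masks treatment or equalizes the two groups.
- *Few cases may be excluded.* Recipients with poor cardiac function and donors with two-quadrant infiltrates are ineligible, which could make some mimics rarer. The exclusion rate is unknown either way.
- *The stakes are limited.* The primary objective is safety, and Section 6 calls the analysis exploratory with no firm conclusions. This lowers the severity. It does not justify leaving an avoidable bias in a named primary efficacy endpoint.

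**Conclusion.** The concern holds in conditional form. The plan does not secure equal, masked classification of PGD in the two groups that it compares. If controls do not receive the same exclusion review, that step is expected to favor nitrite even when the drug does nothing. The illustrated size is 4.5-13.5 points for grade 2-3 or 2.5-7.5 points for grade 3. It rests on an assumed 10-30% exclusion rate, the Pittsburgh row as background, and one-sided application.

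A reader might go further and infer that PGD will fall in the treated group whatever nitrite does. The documents do not support that. Control review is unspecified rather than ruled out, the effect is an expectation and not a certainty with 8 patients, and fuller testing of trial subjects could offset it. The 12.5 points that one patient represents (1/8) is the resolution of the sample, not an estimate of bias.

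The wording should be corrected before the comparison is made. The safety objective is unaffected.

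**What to change.** In Sections 5.7.2 and 5.9:

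1. Base the treated-versus-control comparison on the rule-based grade (PaO2/FiO2, radiograph, extracorporeal or inhaled NO support) before any committee exclusion. Compute it by one algorithm from the same type of source data in both groups. For radiographs, that means clinical reports in both groups or core readings in both.
2. Report the committee-adjudicated grade for the 8 trial patients as supportive.
3. Compare adjudicated grades only if control records go through the same review, masked to treatment and date. In that case report both groups before and after exclusions.
4. Reconcile the endpoint in Section 2.4 (grades 2 and 3) with that in Section 5.9 (grade 3 or greater).

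The cost is mainly wording, since comparing PGD already requires gas, film and support data from control charts. There are two downsides. The rule-based grade counts some lung injury that is not PGD, and not necessarily to the same extent in both groups. Control charts may also be less complete: for example, the D0 gas at FiO2 1.0 and PEEP 5 required in trial subjects may not have been taken. Missing control data should therefore be reported alongside the comparison. Masked review of control charts would remove the first downside, at the price of committee time.
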